4.7 PHARMACOKINETIC AND PHARMACODYNAMIC ANALYSES

Pharmacokinetic and pharmacodynamic (B cells) analyses for ocrelizumab in the breastmilk and serum are described elsewhere for the primary and secondary endpoints (see Sections 4.4 and 4.5).

4.8 SAFETY ANALYSES

The safety outcome measures to be analyzed comprise the following: incidence and nature of all adverse events (AEs), including findings on vital sign measurements, neurological examinations, clinical laboratory tests, and concomitant medications.

All safety analyses will be conducted on applicable data collected from the first postpartum ocrelizumab infusion until the end of the study. The safety analysis will be performed on the SAFM and infants (SAFI) separately.

4.8.1 Exposure of Study Medication

Definitions

Dose: Ocrelizumab dose is given as one infusion or two infusions administered 2 weeks apart. Patients will be considered to have received a Dose of treatment if at least part of one infusion of that Dose (either Day 1 or Day 15 for dual infusions) was given.

Treatment duration (in weeks) for a woman will be calculated as follows:

[(Date of last contact* – Date of first post-partum dose) + 1] / 7

- *Earliest 1) date of last OCR dose plus risk window of 6 months (182 days)
- 2) date of death
- 3) clinical cut-off date

Exposure Analysis

The following measures of exposure of ocrelizumab will be summarized in the SAFM using descriptive statistics:

- Number of patients completing each dose type (Dose 1, full dose; Dose 1 split dose #1; Dose 1, split dose #2)
- Treatment duration (weeks)

- Number of doses received (Day 1 and Day 15 infusions are considered as one dose)
- Total cumulative dose (mg)

A corresponding listing will be produced.

The analysis of exposure to ocrelizumab in infants (as measured via concentration in the breastmilk, and also directly from serum samples) is described previously as part of the primary and secondary endpoints.

4.8.2 Adverse Events

All summaries of AEs will be based on the respective safety population for mothers and infants, and will include AEs occurring between the mother's first post-partum ocrelizumab infusion and the end of the study. Only treatment-emergent AEs (TEAEs) will be analyzed and the terms TEAE and AE will be used interchangeably.

For each recorded adverse event (AE), the term entered by the investigator describing the event (the "reported term") will be assigned a standardized term (the "Preferred Term" [PT]) and assigned to a superclass term (the "System Organ Class" [SOC]) on the basis of the Medical Dictionary for Regulatory Activities (MedDRA) WHO dictionary of terms version 27.1.

Definitions

Treatment-emergent adverse event (TEAE): AEs with an observed or imputed date of onset on or after the start date of trial treatment. If the onset date of the AE is prior to the day of first dose, the AE will be considered treatment-emergent only if the most extreme intensity is greater than the initial intensity (i.e., the intensity for a given AE increases and its end date is on or after the date of the first dose). An AE with a completely missing, non-imputed start date will be assumed to be treatment emergent unless the AE has a complete, non-imputed end date that is prior to the date of the first dose.

Imputation of incomplete date: in order to evaluate if an AE is treatment-emergent, incomplete dates will be imputed as follows:

- o If the start date is incomplete:
 - If the day is missing, impute to 01, or to the day of first dose of ocrelizumab if the month and year is the same as the dosing date.
 - If the month is missing, impute to January, or to the month of first dose of ocrelizumab if the year is the same as the year of dosing.
 - If the date is completely missing, then the date will remain missing
- o If the end date is incomplete:
 - If the day is missing, impute to the last day of the month
 - If the month is missing, impute to December
 - If the date is completely missing, then the date will be missing

If the imputed start date of an AE is post first dose, it is considered treatment emergent. If the imputed start date of an AE is prior first dose, it is considered non-treatment emergent.

In case of a missing start date and an (imputed) end date prior to first dose, the AE is considered non-treatment emergent.

Otherwise, the AE is considered treatment emergent.

Serious Adverse Events (SAEs): all SAEs including serious MS relapses and serious Infusion Related Reactions (IRRs).

Output Conventions

All analyses of AE data will be performed using the PTs unless otherwise specified.

For all summary tables, the AEs will be sorted by SOC (in decreasing order of overall incidence) and then by PT (in decreasing order of overall incidence). At each level of summarization (at least one event, SOC and PT), patients reporting more than one AE will be counted only once. For TEAEs by grade (intensity), the highest grade will be reported. All AE summaries will be based on TEAEs only.

The following summary tables will be generated for mothers and infants separately:

- Overview summary table of TEAEs, including: total number of subjects with at least one AE, total number of AEs, total number of SAEs, total number of deaths, total number withdrawn from study due to an AE, and total number of subjects with at least one:
 - AE with fatal outcome
 - SAE
 - SAE leading to withdrawal from treatment ("Drug Withdrawn" for the "Action taken with ocrelizumab due to SAE/AE" field in the "Adverse Event/IRR" electronic Case Report Form [eCRF] form) (mothers only)
 - SAE leading to dose modification/interruption (mothers only)
 - Related SAE
 - AE leading to withdrawal from treatment (mothers only)
 - AE leading to dose modification/interruption (mothers only)
 - Related AE
 - Related AE leading to withdrawal from treatment (mothers only)
 - Related AE leading to dose modification/interruption (mothers only)
 - AE of Grade ≥3
 - Infusion related reaction (IRR) (mothers only)
 - Serious IRR (mothers only)

- Infections (using the MedDRA SOC of 'Infections and Infestations')
- Serious infections
- Serious infections leading to withdrawal from treatment (mothers only)
- TEAEs, by SOC and PT
- Serious TEAEs, by SOC and PT
- TEAEs, by Highest NCI CTCAE Grade
- Infections, by Type and PT (identified using the Orelizumab specific Adverse Events Glossary of Terms)
- IRRs, by Highest National Cancer Institute (NCI) Common Terminology Criteria for Adverse Events (CTCAE) grade (mothers only)
- Infusion Related Reactions by Time of Event (During Infusion, within 24 hours after end of infusion) Overall and by post-partum Infusion (Dose 1 full dose, Dose 1 split dose 1, Dose 1 split dose 2, Dose 2) (mothers only)
- Adverse Events of Special Interest (AESI, mothers only):
 - Cases of potential medicine-induced liver injury that include an elevated alanine transaminase (ALT) or aspartate transaminase (AST) in combination with either an elevated bilirubin or clinical jaundice, as defined by Hy's law and in the protocol.
 - Suspected transmission of an infectious agent by the study medicine, as defined in the protocol.

All SAEs, AESIs, AEs leading to withdrawal, infections, and deaths occurring during the study will be listed. For all of these listings, mothers/infants pairs will be presented 'next in line' as one row after the other in the same listing, rather than as two separate listings.

4.8.3 Laboratory Data

Laboratory assessments (performed in central laboratory, except for urinalysis) will include the following:

- Hematology (Mother): hemoglobin, hematocrit, quantitative platelet count, red blood cell [RBC] count, white blood cell [WBC] absolute or/and differential count [neutrophils, eosinophils, lymphocytes, monocytes, basophils].
- **Serum chemistry (Mother):** potassium, sodium, chloride, random glucose, AST, ALT, gamma-glutamyl transpeptidase [GGT], total bilirubin and creatinine.
- Urinalysis (Mother): using urine dipstick at site; may include pH, specific gravity, glucose, protein, ketones, blood, and microscopic examination (sediment, RBCs, WBCs, casts, crystals, epithelial cells, bacteria) at the discretion of the investigator.
- **Hepatitis B virus serology (Mother):** Women with positive screening tests for HBV, determined by a positive hepatitis B surface antigen (HBsAg) result (current

infection) or positive hepatitis B core antibody (HBcAb) titers (previous infection) will be excluded. Women with documented history of HBV vaccination or positive HBsAb titers are eligible.

- **Serum immunoglobulin (Ig) concentration (Mother):** Quantitative measurement for IgG, IgM and IgA levels.
- Serum titers (IgG) of antibody immune responses to vaccinations (Infant): May include but not be limited to MMR, DTaP, Hib, HBV and PCV-13; 1 month after the first or second dose of MMR vaccine, or at Month 13 of age (+30 days) if MMR vaccine is not planned to be administered.
- Lymphocyte subtypes (Mother & Infant): Blood samples will be collected to measure B-cell counts (CD19+ and B-cell subsets** [see below]), T-cell counts (CD3+, CD4+, CD8+), and natural killer (NK) cell counts (CD16+CD56+).

**B-cell subsets:

Naïve B cells: CD45+, CD19+, IgD+, CD27-, CD38dim/-

Memory B cells: CD45+, CD19+, CD27+

Unswitched Memory B cells: CD45+, CD19+, IgD+, CD27+ Switched memory B cells: CD45+, CD19+, IgD-, CD27+ Double Negative B cells: CD45+, CD19+, IgD-, CD27-

IgD Transitional B cells: CD45+, CD19+, IgD+, CD27-, CD38^{bright} Plasmablasts/Plasma cells: CD45+, CD19+, CD27+, CD38^{bright}

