4.2 ANALYSIS OF STUDY CONDUCT

Patient disposition information will be summarized separately for the mother and infant, as: the reason and number of screen failures (mother only), the number enrolled, in the respective FAS population, in the respective safety analysis set (SAF) population, completed the treatment and sampling period, discontinued from treatment and sampling period and the reasons for discontinuation, completed the vaccination period, discontinued study and the reasons for study discontinuation.

Disposition information will be listed for mother/infant pairs in a single combined listing.

Mothers and infants who discontinued from the treatment and sampling period will be listed including reasons for discontinuation.

Time on study (weeks) will be summarized for mothers and infants, and calculated as: (date of last assessment* – date of mother's 1st post-partum ocrelizumab dose + 1) / 7.

* Date of last assessment for a subject is defined as the maximum of study completion/discontinuation date and the latest recorded date in all CRF and non-CRF data.

Major protocol deviations, including deviations of inclusion/exclusion criteria, will be summarized in the FAS of mother/infant pairs.

The number enrolled by site and country will be summarized in the enrolled population of mother/infant pairs.

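### The last-contact date that ends maternal treatment duration in SAP 4.8.1 leaves out study exit, so the exposure table can credit a woman with more weeks than she was on study

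*SAP*

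**What the plan says.** SAP 4.8.1 sets out a formula: "Treatment duration (in weeks) for a woman will be calculated as follows", with the expression "Date of last contact* – Date of first post-partum dose) + 1] / 7". The asterisk leads to three dates, of which the first to occur applies: "Earliest 1) date of last OCR dose plus risk window of 6 months (182 days"), then "2) date of death", then "3) clinical cut-off date". No calendar date is given for the cut-off. The result enters the maternal exposure table: "The following measures of exposure of ocrelizumab will be summarized in the SAFM using descriptive statistics". On the regimen, the same section states: "Ocrelizumab dose is given as one infusion or two infusions administered 2 weeks apart".

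SAP 4.2 calculates time on study from the same starting date and with the same plus-one convention, but to the date of last assessment: "Date of last assessment for a subject is defined as the maximum of study completion/discontinuation date" and the latest date found in any data source.

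Protocol 4.6.2 lets women withdraw at any time and names loss to follow-up among the reasons for discontinuation. Protocol 5.1.2.1 collects adverse events up to the last study visit; after that, investigators report only serious events believed to be related to study drug.

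**The concern.** The end date is called last contact, yet none of its three components records a contact or a study exit. When a woman withdraws or is lost, none of the three dates need fall at that moment. The count then runs on to 182 days after her last dose or to the cut-off. The same report can therefore show a treatment duration longer than her time on study.

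The exposure table is the background against which maternal safety is read. Weeks credited after exit are not followed for adverse events in the way earlier weeks were. With a target of at least 10 women, one such record visibly moves the mean.

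**Working it through.** **Inputs.** Formula, 182-day window, death and cut-off: SAP 4.8.1. Time on study: SAP 4.2. Day 0 is the day of the first postpartum infusion, as in the protocol's schedule. Second 300 mg infusion on Day 14: protocol schedule. Dosing every 6 months: Protocol 4.3.2.1. Infant aged 2 to 24 weeks at first dose: Protocol 4.1.1. Final visit at Month 13 of age, with a window of +30 days: Protocol Appendix 1.

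**The plan's own figure.** 6 × 365.25/12 = 182.6 days, which agrees with the stated 182 days (182/7 = 26.0 weeks).

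**Formula.** Duration in weeks = (days from first dose to stop date + 1)/7, where the stop date is the earliest of last dose + 182, death and cut-off.

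**Withdrawal on Day 20, woman alive, nothing recorded later**

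- Time on study: (20 + 1)/7 = 3.0 weeks (2.9 if Day 20 is the SAP's analysis day, which starts at 1).
- One infusion, cut-off at least 182 days after first dose: (182 + 1)/7 = 26.1 weeks, 8.7 times her time on study.
- Second infusion on Day 14, cut-off at least 196 days after first dose: (14 + 182 + 1)/7 = 28.1 weeks, 9.4 times.

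**Dependence on the cut-off.** Its date is not stated, so a range is assumed (one infusion):

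| Cut-off, days after first dose | Calculation | Weeks credited |
|---|---|---|
| 60 | 61/7 | 8.7 |
| 90 | 91/7 | 13.0 |
| 120 | 121/7 | 17.3 |
| 182 or more | 183/7 | 26.1 |

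**Effect on the mean.** One such woman among 10 adds (26.14 − 3.00)/10 = 2.3 weeks, or (28.14 − 3.00)/10 = 2.5 weeks with the second infusion. The documents give no withdrawal rate, so one in 10 is an illustration.

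**Completers with a second postpartum dose.** The schedule documents such a dose at Visit 7, and SAP 4.8.2 tabulates infusion reactions for it. Assume that it is given at Day 182 and that the cut-off is at least 364 days after the first dose. The formula gives (182 + 182 + 1)/7 = 52.1 weeks. Month 13 of age is 13 × 365.25/12 = 395.7 days.

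- Infant 24 weeks old at first dose: time on study (395.7 − 168 + 1)/7 = 32.7 weeks, or 37.0 weeks if the 30-day window is used in full. The excess is about 19 or 15 weeks.
- Infant 2 weeks old at first dose: (395.7 − 14 + 1)/7 = 54.7 weeks. There is no excess.

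Protocol 3.2 expects enrolment over about 21 months, so a common final cut-off could fall well after an early participant's exit.

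**The case against.** The best defence is that the rule is a deliberate exposure window. The SAP calls it a risk window, and its length matches the 6-monthly dosing interval. Protocol 3.3.2 gives a mean terminal half-life of 26 days, a longest recorded value of 53 days, and elimination by about 4.5 months. A woman who leaves on Day 20 still carries drug. Observed time is reported separately under SAP 4.2, and two measures with different purposes may differ.

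Part of this stands: a pharmacological window is a legitimate quantity. It does not explain the rule as written. The label speaks of contact, and the list already stops at the clinical cut-off, which limits observation and not drug persistence. The rule thus stops at the end of data for some women but not for those who leave.

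A reader might also infer more than the documents support:

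- *That adverse events will look rarer per unit of exposure.* SAP 4.8.2 counts events and women with at least one event; it has no person-time rate. Protocol 6.6.1 mentions incidence rates without a denominator, and SAP Section 4 states that the SAP's analyses take precedence. Nor is the direction fixed. A completer with one infusion has 26.1 weeks of treatment duration against 32.7 to 54.7 weeks on study, so dividing by the former would make her events look more frequent.
- *That nothing can be reported after exit.* Related serious events still are (Protocol 5.1.2.1).
- *That early leavers are the women most likely to have had a problem.* Nothing in the documents shows this, and the protocol separates stopping treatment from leaving the study.
- *That the window is wrong for women who start another disease-modifying therapy.* Ocrelizumab exposure does not end on that date. Switches are recorded (Protocol 4.6.1), and concomitant medications are summarized and listed (SAP 4.8.5).

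**Conclusion.** The definition does not match its label and allows maternal treatment duration to exceed time on study. For a Day 20 withdrawal the figure is 26.1 to 28.1 weeks against 3.0, provided that the cut-off falls at least 182 or 196 days after the first dose; it shrinks with an earlier cut-off. Among completers with a second dose, the excess runs from none to about 19 weeks under the assumptions shown.

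The consequence is small. The measure is descriptive, feeds neither co-primary endpoint, and changes no planned adverse event table. It would distort event rates only if it were used as a person-time denominator, which the SAP does not specify. It is still worth correcting, because a reported exposure figure would be wrong on its face and the remedy is simple.

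**What to change.** In SAP 4.8.1, add a fourth stopping date: study discontinuation or last recorded assessment, as defined in SAP 4.2. The Day 20 case then gives 3.0 weeks and the late second-dose completer 32.7, while a completer with one infusion keeps 26.1.

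If a pharmacological risk window is wanted as well, report it as a separate row under that name. Should adverse event incidence rates be produced, state that they use observed time.

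The cost is one line of text and one changed derivation. Discontinuation dates already feed SAP 4.2, so no new data are needed. Mean treatment duration will fall if any woman is affected. No additional output for women who switch therapy is required.

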- ^{cc} A structured telephone interview will be conducted by site personnel postpartum every 2 weeks during the treatment and sampling period and every 3 months during the vaccination period (in-between ocrelizumab infusions) for a general review, and to identify and collect information on any changes in the woman's and infant's health status (including the occurrence of MS relapses in the mother and use of new concomitant medications) and possible adverse events in both the woman and the infant (particularly infections); women will also be asked if the ASQ-3 form is being filled out. No telephone contact is needed in weeks where the woman is performing on-site visits.
- dd Adverse events in both mother and infant will be reported throughout the study as per standard pharmacovigilance procedures. Adverse events will also be captured at screening for women who received ocrelizumab before pregnancy.
- ee Documentation of premedication is not required.

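### With a partial start date, SAP 4.8.2 flags some adverse events that ended before first dose as treatment-emergent, and contradicts itself on pre-dose events that worsened

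*SAP*

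**What the plan says.** SAP 4.8.2 limits the AE summaries to the span from the first post-partum infusion to the end of the study, and analyses treatment-emergent events only. Its rules are as follows.

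- **Definition.** Treatment-emergent events are "AEs with an observed or imputed date of onset on or after the start date of trial treatment". For an onset before first dose, "the AE will be considered treatment-emergent only if the most extreme intensity is greater than the initial intensity", which the SAP explains as: "the intensity for a given AE increases and its end date is on or after the date of the first dose".
- **Start date completely missing.** "An AE with a completely missing, non-imputed start date will be assumed to be treatment emergent unless the AE has a complete, non-imputed end date", meaning one before first dose.
- **Start date partial.** "If the day is missing, impute to 01, or to the day of first dose of ocrelizumab if the month and year is the same" (the comparison is with the month and year of dosing). A missing month becomes January, or the dosing month if the year is the dosing year. Neither rule refers to the end date.
- **End date partial.** The last day of the month; December if the month is missing.
- **Classification after imputation.** A start imputed to after first dose is treatment-emergent. For an earlier one, "If the imputed start date of an AE is prior first dose, it is considered non-treatment emergent". A missing start with an end date before first dose, imputed or not, is non-treatment-emergent. Everything else is treatment-emergent.

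**The concern.** An event with a known end date before the infusion cannot have begun after it, yet the partial-date rule can place its start on the dosing day. The SAP uses the end date to exclude such an event when the start is completely missing, so a record that carries more information is classified less accurately than one that carries less.

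For a pre-dose event that worsened after dosing, the definition and the imputation rules point in opposite directions once the start date is partial. Protocol Appendix 5 (A5-3.4) has a persistent event recorded once, with its initial and its most extreme severity. There is then no second record with a post-dose start to pick up the worsening.

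Pre-dose events do reach the database. The schedule of assessments marks AE assessment at screening, and its footnote adds: "Adverse events will also be captured at screening for women who received ocrelizumab before pregnancy". What is at stake is the AE counts and incidences, in a study of at least 10 mother-infant pairs.

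**Working it through.** The SAP gives no figure on this point, so the check applies its rules to test records. The first dose is assumed to be 20 March 2024; all dates are illustrative. TE means treatment-emergent.

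| Start | End | Worsened | Imputed start | By the definition | By the imputation rules |
|---|---|---|---|---|---|
| Mar 2024 | 10 Mar 2024 | no | 20 Mar 2024 | TE | TE |
| 2024 | 15 Feb 2024 | no | 20 Mar 2024 | TE | TE |
| 5 Mar 2024 | 10 Mar 2024 | no | not needed | not TE | not needed |
| missing | 10 Mar 2024 | no | none | not TE | not TE |
| Feb 2024 | 25 Feb 2024 | no | 1 Feb 2024 | not TE | not TE |
| Feb 2024 | 30 Apr 2024 | yes | 1 Feb 2024 | TE | not TE |
| 2023 | 30 Apr 2024 | yes | 1 Jan 2023 | TE | not TE |
| 10 Feb 2024 | 30 Apr 2024 | yes | not needed | TE | not needed |
| Mar 2024 | 30 Apr 2024 | yes | 20 Mar 2024 | TE | TE |
| missing | Feb 2024 (imputed 29 Feb) | no | none | TE | not TE |

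**Ended before dosing.** In rows 1 and 2 the imputed start falls after the recorded end, by 10 days in row 1 (20 − 10), and both sets of rules give TE. Rows 3 and 4 show that a pre-dose event ending on the same date is not TE when its start is fully dated or wholly missing. Row 5 marks the limit: a partial start in an earlier month is handled correctly. Row 2 assumes that the month rule is applied before the day rule; row 1 does not depend on that order.

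**Worsened after dosing.** In rows 6 and 7 the definition gives TE and the imputation rules give not TE. Row 8 is the row 6 event with its start day known, and it is TE. Row 9 marks the limit: a partial start in the dosing month moves to the dosing day and is kept.

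**A further conflict.** In row 10 the definition demands a complete end date before it will exclude the event, whereas the imputation rules accept an imputed one.

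**Size.** One subject in about 10 is 1/10 = 10 percentage points. This is a ceiling, because SAP 4.8.2 counts a subject once at each level (any event, system organ class, preferred term). The incidence at a level moves only if the subject has no other event there.

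**The case against.** Placing an ambiguous start on the dosing day is deliberately conservative, and the opening of SAP 4.8.2 already confines the summaries to events from the first infusion onward. The first argument fails where the end date is known, because nothing about timing is then ambiguous. The second shows what was intended, but the flag is what a programmer will derive, and it disagrees with that intent.

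On worsened events, a reader might infer that they certainly vanish from every treatment-emergent table. The documents do not support that. The definition expressly covers imputed onsets, so on one reading the event stays in; the outcome is undetermined. Protocol A5-3.9 also narrows the case: a condition present at the baseline visit goes to medical history and becomes an AE only if it worsens during the study. What remains is mainly events already recorded as AEs at screening that persist past dosing. The SAP's listings of SAEs, infections and deaths during the study are not expressly tied to the flag, so such events may still be seen there.

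A reader might also suppose that partial dates will be common because many AEs are gathered by telephone recall. The schedule marks telephone interviews only from Day 1 after the infusion, so they are not how screening-period events are collected. The screening footnote names only mothers with prior ocrelizumab, although the schedule row itself carries no such restriction.

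**Conclusion.** Both defects follow from the text of SAP 4.8.2, within limits.

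- **Event ended before first dose.** It is wrongly flagged when the day is missing in the dosing month. The same happens when the month is missing in the dosing year, if the month is imputed before the day.
- **Worsened pre-dose event.** This is an internal contradiction to be reconciled, not a settled omission. It arises only when the imputed start falls before first dose.

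Frequency should be low; the documents give no rate of partial dates from which to estimate it. The co-primary endpoints are unaffected. The most that one misclassified subject can do to an incidence is about 10 percentage points, assuming about 10 subjects in the safety set. This is a minor correction, worth making because a known pre-dose event should not be tabulated as on-treatment and because two programmers could derive different flags from the same record.

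**What to change.** In SAP 4.8.2:

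1. Apply the end-date check to partial as well as missing start dates. If the end date, complete or imputed to its latest possible value, is before first dose, the event is not treatment-emergent. Never impute a start later than the end date. The existing end-date rules already give the latest possible value, so an event that might have run past first dose is still kept.
2. Add to the sentence on imputed starts before first dose: *unless the most extreme intensity exceeds the initial intensity and the end date is on or after first dose*.

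When applied to the test records, these changes turn rows 1 and 2 to not TE and rows 6 and 7 to TE. They settle row 10 as not TE and leave the fully dated rows unchanged. The cost is two sentences of SAP wording and a small change to the derivation, with no new data.
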